Assessments of primary and secondary outcome measures will occur at the time points

diagramed in Figure 5. Details regarding the specific assessment tools and measures to be used are described below and listed in **Table 2**. The primary outcome variables for Aim 1 (Spinal Cord Injury Pain Instrument (SCIPI)⁸⁰ score of ≥ 2 , and Neuropathic Pain Symptom Inventory score⁸⁹) will be collected during each scheduled assessment (full and abbreviated assessments), with additional outcome measures recorded less frequently (during full assessment sessions only: 4 times during the study).

Randomization and blinding procedures:

A blocked randomization procedure will be used, so that for each eight patients enrolled, four will be allocated to TENS and four to Sham TENS. A computer-generated random assignment sequence will only be accessible to the study staff member responsible for delivering TENS treatments. The PI of the study, the researchers evaluating pain diagnoses, and the research subject will not be informed of the treatment allocation assigned. All subjects will be told that they may or may not feel the stimulation from the TENS unit during treatment sessions due to the parameters of the study. The stimulation parameters of the TENS unit will not be visible to the subject, so that subjects will not obviously know to which study group they were randomized.

Treatment procedures:

(a) *TENS device*: The TENS 7000 Dual Channel battery-powered digital stimulator (Roscoe Medical, Ohio, USA) will be used. This device provides for adjustable frequency/pulse rate, pulse width, and amplitude, as well as recording of session data (settings and duration of treatment session). The TENS 7000 device has two channels. Each channel will be connected to two self-stick square electrodes (thus, a total of 4 electrode pads will be used) with dimensions of 2 inches by 2 inches. New electrode pads will be used for each treatment session.

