(a) *Assessment procedures*: **Table 2** lists measures that will be collected during full and abbreviated assessments, as well as before and after each TENS session. Full assessment sessions will occur at three time points: baseline (prior to treatment initiation); termination of the 8-week treatment protocol; and 12 months post-injury. The full assessment protocol will require approximately 180 minutes to complete and may be completed in multiple sessions due to participant availability. An abbreviated assessment protocol will be administered at the 4-week treatment time point (i.e., halfway through the full series of treatment sessions), and over the phone each month after treatment has ended, until the 12-month post-injury time point. The abbreviate assessment will require 30 minutes to complete. In addition, numerical ratings of pain and the Neuropathic Pain Symptom Inventory⁸⁹ will be assessed before and immediately after each 30-minute TENS session. (It is expected that, for most patients, pain ratings will be “0,” as many will not have developed neuropathic pain symptoms in the first few months after injury when TENS is being administered. Collection of this information is important in order to insure that TENS is not related to any increase in pain symptoms during treatment.) Adverse events/ side effects will also be captured at the end of each TENS session. The assessment schedule is depicted by the blue and yellow boxes at the bottom of **Figure 5**.

Table 2: List of assessment tools to be used

Assessment domain	Assessment	Full assessment	Abbreviated assessment	Treatment sessions
Pain classification	SCIP, and ISCPBDS2	X	X	
Pain intensity and symptoms	NRS for pain ISCPBDS2	X	X	X

	ISCIPEDES [“pain symptoms” subset]	X		
	NPSI	X	X	X
	sf-MPQ-2	X		
Maladaptive pain coping	PCS	X		
Sensory function	ASIA sensory scores*	X		
	QST	X		
Emotional function	PHQ-9*	X	X	
	SCI-QOL Resilience scale – short form *	X	X	
Treatments	Frequency, dose, effectiveness (from ISCIPEDES)	X	X	
Adverse events	Incidence and severity			X
Time required (minutes)		120	30	5

* measures/assessments that overlap with national database Form I/II

** assessments that will only be carried out at 12-months post-injury

(b) *Assessment tools:* Copies of all instruments to be used are uploaded within the eProst UM-IRB application for this study.

i. Pain classification:

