- The Spinal Cord Injury Pain Instrument (SCIPI)⁸⁰ will be used to identify pains that are likely to be neuropathic in nature. This four-item questionnaire has shown sensitivity and specificity of 78% and 73%, respectively, for diagnosing neuropathic pain when using a cutoff score of ≥ 2 on this scale.⁸⁰ The pain classification definitions and guideline presented within the International SCI Pain Basic Data Set 2 (ISCIPIBDS2) will also be used to assist with classification of pain type.

This assessment will be used as the primary outcome measure for Aim 1, indicating the presence or absence of neuropathic pain at each follow-up time point.

ii. Pain intensity and symptoms:

Based on differentiated pains, as reported by the study subject, the intensity of each pain will be rated using a 0 – 10 numerical rating scale (NRS), with 0 being equal to “no pain” and 10 being equivalent to “pain as bad as you can imagine.” Subjects will be asked to “Rate your pain by indicating the number that best describes your pain on average over the past 24 hours,” “over the past week,” and “over the past 3 months.”

This scale, including the phrasing of the anchors and the recall time points, has been suggested as a primary

endpoint for chronic pain clinical trials.⁹² *Changes in pain intensity for neuropathic pains will be calculated across the assessment time points to measure the effectiveness of TENS treatment for those who present with neuropathic pain at baseline [Aim 1], and to assess correlations among pain severity and demographic and psychological factors [Aim 2].*

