- *The Neuropathic Pain Symptom Inventory (NPSI)⁸⁹ will be used to quantify the severity of neuropathic pain-specific characteristics. This questionnaire has been validated and used in a number of patient populations with various neuropathic pain conditions^{89, 95-98} including those with SCI.^{8, 74} A total NPSI score will be calculated as an indication of the severity of neuropathic pain.⁸⁹ This questionnaire should be distinguished from the SCIPi, which is also used for neuropathic pain, but is intended as a dichotomous *diagnostic screening tool* for neuropathic pain in SCI, whereas the NPSI is intended as an ordinal *measure of neuropathic pain severity. For those subjects with neuropathic pain symptoms at entry into the study, the NPSI total score will be used to determine whether a reduction in neuropathic pain severity is present after TENS treatment, and during longitudinal follow-up [Aim 1]. This measure will also be used to examine associations between neuropathic pain severity and demographic and psychosocial factors [Aim 2].**
- We will also capture specific information about the presence and severity of different qualities of the pain experience for each pain location the subject describes using the short-form McGill Pain Questionnaire 2 (SF-MPQ2)⁹⁹ as secondary outcome measures of sensory and affective components of pain. The SF-MPQ2 is a revised version of the SF-MPQ¹⁰⁰ to include both qualities of pain associated with nociceptive pain types and those associated with neuropathic pain types. Desirable psychometric properties of the SF-MPQ2 have been documented in a number of pain patient populations.^{99, 101-103} *Responses to specific pain qualities will assist with pain diagnosis, and total scores and subscale scores of “continuous pain,” “intermittent pain,” “neuropathic pain,” and “affective descriptors” will be used in secondary analyses of TENS effectiveness [Aim 1] and relationships with other outcomes of interest [Aims 2].*

iii. Maladaptive pain coping:

- The Pain Catastrophizing Scale (PCS)¹⁰⁴ measures the degree to which individuals engage in a maladaptive pain coping style that is characterized by exaggerated and ruminating negative cognitions and emotions during painful situations. The PCS has demonstrated high validity and reliability.¹⁰⁵ *Measures obtained from the PCS will be used to prospectively track its potential as a pre-disposing factor for the development of chronic pain after SCI [Aim 2].*
- iv. Sensory function:

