Based on a total sample size of 98 subjects, and an estimated 15% drop-out rate, we expect that approximately 82 subjects will complete the study (i.e., 41 subjects per treatment arm). Based on previous work,^{21, 59} we project that 60% of subjects in the Sham TENS (control) group will have at- or below-level neuropathic pain at the 12 month follow-up time point. Thus, with 41 subjects in each group, $\alpha = 0.05$, power of at least 80%, and an analysis based on a two-sided Z-test (for group difference in proportion of subjects with neuropathic pain) for *Hypothesis 1a*, we will be able to detect at least a 50% reduction in the rate of subjects with chronic neuropathic pain in the TENS treatment group compared to the Sham group at 12 months post-SCI (i.e., Sham TENS = 60% with neuropathic pain; Treatment TENS = 30% neuropathic pain).

For t-test analyses assessing differences between groups (Sham vs. Treatment) using continuous variables (e.g., NRS, NPSI), 41 subjects in each group will allow for detection of a medium-to-large effect size (i.e., Cohen's $d = 0.6$) with α set at 0.05 and power of 0.80. Paired correlations will also be used for additional analyses (*Aim 2*). For correlations within group ($n = 41$), with power set at 0.80 and $\alpha = 0.05$, we will be able to detect a medium-to-large effect size (i.e., Cohen's $f^2 = 0.20$), and we will be able to detect a small-to-medium effect size for across-group analyses ($n = 82$; Cohen's $f^2 = 0.10$).

Data analysis plan:

Descriptive evaluations of the data will be performed for all variables to check the integrity of the data and to verify the underlying assumptions of the statistical tests that are planned. If necessary, and as appropriate, data will be transformed prior to any parametric analyses, or non-parametric techniques will be used with untransformed data. Statistical analyses will use two-tailed tests and an a-priori α of 0.05.

In addition to direct tests of hypotheses (described in detail below), descriptive analyses and graphical representations (e.g., spaghetti plots) of data will be used to describe longitudinal

characteristics of clinical pain, somatosensory function, and other physical and psychological outcomes across the 12-month timeline of study participation.

Hypothesis 1a:

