The primary statistical analysis, to test the effectiveness of prophylactic TENS for neuropathic pain after SCI will be via a two-proportion z test, comparing the percentage of subjects in the TENS treatment group who are “positive” for neuropathic pain at 12 months post-injury to the percentage of subjects in the Sham TENS group who are positive for neuropathic pain at 12 months post-injury. Subjects who score a 2 or more on the SCIPPI for a pain located at or below their neurological level of injury at the 12 month follow-up time point will be considered positive for neuropathic pain. Subjects who do not have a pain at- or-below the level of injury or a score of 2 or more on the SCIPPI will be considered negative for neuropathic pain. For those subjects who have neuropathic pain symptoms early after injury (i.e., prior to entering the study), a “positive” result for neuropathic pain will be defined as having neuropathic pain that is moderate or greater (rated at least a 4 out of 10) at the 12 month follow-up assessment.

Additional analyses will be conducted using secondary outcomes collected at the 12-month time point: 1) comparison of pain severity (using the NRS and NPSI scores) between the groups (This analysis will be especially important if the primary analysis does not show a difference in rates of the presence of neuropathic pain at 12 months.); 2) comparison of use of analgesics between groups; and 3) comparison of response to pain interference questions from the ISCPBDS2. General linear model analyses will be used, with TENS group (Treatment vs. Sham) as a categorical predictor of these secondary outcome measures.

Separate analyses for at-level neuropathic pain and below-level neuropathic pain, as well as nociceptive pains, will also be conducted to examine whether TENS differentially impacts their development or severity. Additional analyses will be conducted, using the diagnosis of each pain type according to ISCPBDS guidelines, as determined and agreed upon by our study staff pain experts, as a confirmation of the primary neuropathic pain metric (SCIPPI ≥ 2).

Hypothesis 1b:

To investigate factors that may be related to patient responsiveness to TENS as a preventive treatment for chronic neuropathic pain, we will assess correlations between changes in evoked pain (before and after TENS treatments) and the presence and severity of neuropathic pain

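### The 12-month severity comparison names treatment group as its only predictor, although baseline total NPSI is collected in every subject and randomisation is not stratified on entry pain

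*Combined protocol and SAP*

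**What the plan says.** Section 8 lists two primary endpoints at 12 months: presence of chronic neuropathic pain, and its severity. Section 11, Hypothesis 1a, places the severity comparison (NRS and NPSI) among secondary outcomes but gives it particular weight if the rates do not differ. The model sentence is: "General linear model analyses will be used, with TENS group (Treatment vs. Sham) as a categorical predictor of these secondary outcome measures". The Power / sample size text treats the same outcomes as unadjusted: "For t-test analyses assessing differences between groups (Sham vs. Treatment) using continuous variables (e.g., NRS, NPSI".

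On baseline data, section 9 (Overview) says the Aim 1 outcome variables, NPSI included, "will be collected during each scheduled assessment (full and abbreviated assessments". Baseline is a full assessment, and under Assessment tools "A total NPSI score will be calculated as an indication of the severity of neuropathic pain". NRS is different: "Based on differentiated pains, as reported by the study subject, the intensity of each pain will be rated", and over three recall windows, so the plan defines no single NRS value per subject.

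The Overview randomises subjects whether or not they have neuropathic pain at entry. Allocation is in blocks of eight with no stratification factor.

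Baseline severity is used elsewhere, for subjects symptomatic at entry: "Changes in pain intensity for neuropathic pains will be calculated across the assessment time points to measure the effectiveness of TENS treatment". The Overview and the NPSI entry say much the same. None of these names a model.

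**The concern.** Entry pain is an obvious candidate predictor of 12-month pain. The plan itself treats it as relevant, because Hypothesis 1a applies a different rule for a positive primary result to subjects symptomatic at entry. The severity model has no corresponding term, and the randomisation does not balance the arms on it. A group-only model leaves any variance explained by baseline in the error term, and it lets a chance difference in entry pain pass into the estimate. If adjustment is not prespecified, the choice may also be made after the 12-month data are seen. The stakes are the precision of a comparison that section 8 calls primary, and how far it can be trusted if the arms happen to differ at entry.

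**Working it through.** **Inputs from the documents (section 11):** 41 completers per arm, d = 0.6, two-sided alpha 0.05, stated power 0.80. Projected 12-month prevalence is 60% in Sham and 30% in TENS. **Assumed:** the baseline to 12-month correlation r and, above 15%, the share symptomatic at entry.

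**1. The plan's own figure.** Noncentrality = d × √(n/2) = 0.6 × √20.5 = 2.717 on 80 df, giving power 76.5%. The effect detectable with 80% power is d = 0.626 (t) or 0.619 (normal approximation). Both round to the stated 0.6.

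**2. ANCOVA, normal scores.** Noncentrality = [d/√(1 − r²)] × √(n/2) / √(1 + F/(2n − 2)) on 79 df, averaged over F ~ F(1, 2n − 2) to allow for chance covariate imbalance.

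| r | 0 | 0.1 | 0.2 | 0.3 | 0.4 | 0.5 |
|---|---|---|---|---|---|---|
| Power, % | 76.0 | 76.4 | 77.7 | 79.8 | 82.9 | 86.8 |

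Break-even with 76.5% is at r of about 0.11.

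**3. With a floor at zero.** Section 9 expects most pain ratings during treatment to be zero, "as many will not have developed neuropathic pain symptoms in the first few months after injury when TENS is being administered". A bivariate normal was therefore censored at zero, with 60% of Sham and about 33.5% of TENS above zero at 12 months (latent shift 0.68 SD) and 20,000 trials per cell. Change in power, in percentage points, linear ANCOVA minus group-only (group-only power 71.7 to 72.9%):

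| Above zero at baseline | latent r = 0 | 0.2 | 0.3 | 0.4 | 0.5 |
|---|---|---|---|---|---|
| 15% | -0.6 | -0.2 | +0.8 | +2.3 | +4.5 |
| 25% | -0.5 | -0.1 | +1.0 | +2.8 | +5.2 |
| 40% | -0.4 | +0.3 | +1.6 | +3.5 | +6.9 |

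The 15% is 25% (share of one-year cases already symptomatic at one month, section 9) × 60%. Moving to ranks without a covariate gains about 4 points. Rank ANCOVA then gives 77.4 to 77.7% at latent r = 0.3 (rank group-only 75.9 to 76.9%) and 79.9 to 82.7% at 0.5 (rank group-only 76.1 to 76.7%). Rejection under the null was 4.8 to 5.2% for all four tests.

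**4. Chance imbalance in entry pain.** Taking two independent binomials (41, b), a difference of 5 or more subjects (5/41 = 12 percentage points) has probability 16%, 25% and 31% at b = 15%, 25% and 40%. The resulting shift in the unadjusted estimate is ρ × (5/41)/√(b(1 − b)), where ρ is the assumed correlation of entry pain with the 12-month score. That is 0.068, 0.056 and 0.050 SD at ρ = 0.2, and 0.102, 0.084 and 0.075 SD at ρ = 0.3. The standard error of the difference is √(2/41) = 0.22 SD.

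**5. Subjects symptomatic at entry.** The same prevalences give about 6, 10 and 16 per arm. At d = 0.6, r = 0.3 and equal variances:

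| Per arm | 12-month score only | Change score, d/√(2(1 − r)) | ANCOVA |
|---|---|---|---|
| 6 | 15.6% | 12.5% | 15.4% |
| 10 | 24.6% | 18.9% | 25.3% |
| 16 | 37.6% | 28.4% | 39.5% |

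**The case against.** The strongest reply is that nothing is wrong with the planned test. It is unbiased over randomisation and holds its type I error. That stands: a reader might infer bias or invalidity, and the documents support neither.

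The sentence calls group a categorical predictor in a framework that admits covariates, and it does not say that group is the only one. That also stands, so the defect is lack of prespecification, not a prohibition. Nor does the plan ignore baseline altogether, since change from baseline is planned for subjects symptomatic at entry.

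A reader might infer that adjustment closes a shortfall between 76.5% and the stated 80%. It should not be argued that way: the stated d = 0.6 is a rounding of 0.626 and has nothing to do with baseline.

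A reader might also infer a likely gain of several points. No such value can be derived. Let q be the prevalence of entry pain, with 60% positive at 12 months and 25% of those already symptomatic early. The correlation of the two presences is then φ = (0.15 − 0.60q)/√(0.24q(1 − q)). This is 0.34 at q = 15%, 0.15 at 20%, 0 at 25% and negative at 40%. It concerns presence rather than severity, and uses a one-month figure while treatment may start up to four months after injury. Still, it shows that a positive correlation is not assured.

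The imbalance effect is modest too: under half a standard error for a 5-subject difference, and zero on average. Finally, the plan already allows a remedy for skewed scores: "If necessary, and as appropriate, data will be transformed prior to any parametric analyses, or non-parametric techniques will be used with untransformed data". On these simulations, ranks alone gain more than the linear covariate does at latent r of 0.4 or below. That supports naming the rank version in advance; it does not remove the case for the covariate, which adds to it when r is positive.

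**Conclusion.** The point holds as a recommended improvement in efficiency and prespecification. The all-subjects severity model names group alone, while a baseline value of the same score is available for every subject and allocation is not stratified on entry pain. The worst-case cost of adjusting is about 0.5 power points. The possible benefit depends on an undocumented correlation: from 76.5% to between 76.0% and 86.8% with normal scores over r = 0 to 0.5, or a change of about -0.6 to +7 points with the expected floor over latent r = 0 to 0.5. It may be small or nil, and no likely value is claimed. Adjustment also protects against a chance difference in entry pain within this particular trial. For subjects symptomatic at entry, power is about 40% or less by any method under the assumptions shown. ANCOVA beats a simple change score there, but at 6 per arm it does not beat the 12-month score alone. The inconsistency over whether severity is primary or secondary adds weight to the comparison but is a separate matter.

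**What to change.** - **NPSI.** Prespecify ANCOVA of 12-month total NPSI on treatment plus baseline total NPSI, in all randomised subjects with a 12-month value.
- **Floor.** Name in advance a rank-based version (ranks of both scores) and the condition for using it if scores pile up at zero.
- **Sensitivity.** Keep the unadjusted comparison as a sensitivity analysis.
- **Symptomatic at entry.** Where these subjects are analysed separately, use the same baseline-adjusted model instead of a simple change score, and state that power is low.
- **NRS.** Adjust for baseline neuropathic-pain presence, unless a single subject-level NRS score is first defined; in that case treat it as for NPSI.
- **Primary test.** The two-proportion z-test is unchanged.

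For NPSI the cost is wording in the analysis plan, including the rank version and its condition, with no new data, and about 0.5 power points if baseline predicts nothing. For NRS, a subject-level definition is extra work if that route is taken.

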Increasing age and minority status have generally been found to increase the presence and severity of various chronic pain conditions.^{54, 55} Support for a relationship between older age and chronic pain status in those with SCI has also been reported,⁵⁶ but whether this age-pain relationship differs depending on the type of chronic pain (neuropathic or nociceptive) has received little attention. Similarly, differences in pain severity between Whites/Caucasians with SCI and non-White patients with SCI have been documented,^{57, 58} but whether race influences the presence and severity specifically of neuropathic pain after SCI is not clear. Additionally, because of imbalanced frequencies of subjects across different racial and ethnic groups, these studies have simply compared Whites to non-Whites, pooling all minority groups together as though they were one homogenous group. The diversity of the South Florida community allows for a relatively more balanced representation of persons with SCI across minority and non-minority groups (i.e., 37% Black/African American; 34% Hispanic; 53% White, in our previous spinal cord injury subject samples). Thus, comparison among minority groups will be possible. Indeed, results from our center (see “Preliminary data,” below) suggest greater rates of the presence of chronic nociceptive pain in Black/African Americans, and greater rates of the presence of chronic neuropathic pain in persons with a Latino or Hispanic background.⁵⁹

Pain catastrophizing, depressive symptoms, and low resilience as risk factors for neuropathic pain (Psychological risk factors):

Because pain is defined as a “sensory and *emotional* experience,”¹ it is not surprising that psychosocial factors, including pain coping style, depression, and resilience characteristics, have been linked to pain intensity and impact.⁶⁰⁻⁶⁷ Some studies have looked at these factors and their relationship to pain specifically in persons with SCI,^{8, 68} but: 1) whether these psychological factors predict pain development and severity *differentially* for neuropathic pain and nociceptive pain after SCI; and 2) the covariance of these factors with specific types of pain (neuropathic, nociceptive) *across time* during the first year after SCI have not been well documented in SCI. Thus, we will collect assessments of depression, pain catastrophizing, and resilience at baseline

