symptoms at the 12 month post-injury time point. It is anticipated that those who show reduced sensitivity to noxious stimuli after TENS treatments will exhibit a lower risk for chronic neuropathic pain. A repeated measures regression analysis, including appropriate covariates (e.g., demographic and injury-related factors, concomitant treatments, amplitude setting of TENS treatments), will assess whether changes in evoked pain sensitivity will be a significant predictor of neuropathic pain at 12 months post-injury in the TENS treatment group.

Hypotheses 2a, 2b, and 2c:

Chi square analyses, t-tests, and correlations across all subjects (with TENS group assignment as a covariate) will be used to separately examine whether demographic variables (age and minority status), psychological characteristics (pain catastrophizing, depressive symptoms severity, and levels of resilience), and measures of evoked pain sensitivity (pain thresholds and ratings of suprathreshold noxious stimuli) measured at baseline can predict the presence and severity of chronic neuropathic pain at 12 months post-SCI. Separate sub-analyses will also be conducted with regard to the impact of these factors on pains with different diagnostic categories (nociceptive pain, neuropathic pain).

Data security / Quality control:

All research personnel will complete and maintain trainings regarding privacy and data security as required. All personnel will receive training regarding all study procedures as required for their role, as assigned and overseen by the PI, to insure data quality and integrity of the science.

Data for the study will be recorded on paper, using the most-updated and approved study forms. These paper documents will be stored in locked file cabinets in rooms 3.156 and 3.153B of the Christine E. Lynn Rehabilitation Center ([name]). This room is locked and is accessible only by those who have been given card access. These paper documents will be stored for at least 3 years after the final termination of the grant.

Data from the paper documents will be entered into a password protected electronic database that will receive periodic and thorough data quality checks through established procedures. This

electronic file will not contain any personally-identifiable information, and will be maintained for at least 3 years after the final termination of the grant.

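### The plan asks whether TENS affects at-level, below-level and nociceptive pain differently, but specifies only separate analyses by pain type and no direct test of a difference

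*Combined protocol and SAP*

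**What the plan says.** Section 11, Data analysis plan, Hypothesis 1a: after the primary two-proportion test and the listed secondary comparisons, the plan adds separate analyses for three pain types, which "will also be conducted to examine whether TENS differentially impacts their development or severity". The general linear models described just before have treatment group as their only named predictor. The general rule for all tests is "Statistical analyses will use two-tailed tests and an a-priori α of 0.05", with no adjustment for these analyses.

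The Preliminary data part of section 3 reports that most people with chronic pain after spinal cord injury have more than one pain.

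Aim 2 has a related but looser pair of statements. The psychological risk factor part of section 3 notes as an open question "whether these psychological factors predict pain development and severity" differentially for neuropathic and nociceptive pain. For Hypotheses 2a to 2c, section 11 then says: "Separate sub-analyses will also be conducted with regard to the impact of these factors on pains with different diagnostic categories".

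Neither place names a treatment-by-pain-type term, a predictor-by-pain-type term, or a criterion for concluding that two effects differ.

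**The concern.** A differential effect is a contrast between two effects. Separate analyses estimate each effect but do not test the contrast. One result below 0.05 and another above it is weak evidence that the effects differ, particularly when power per type is moderate. Because the outcomes come from the same subjects, the contrast is partly within subject, and separate analyses give no standard error for it.

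At stake is a statement such as TENS preventing at-level but not below-level pain. As the plan stands, such a statement would have no error control, and it could steer the design of later trials.

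**Working it through.** **Inputs from the documents** (section 11, Power / sample size): 41 completers per arm; two-sided alpha 0.05; design rates "Sham TENS = 60% with neuropathic pain; Treatment TENS = 30% neuropathic pain", a relative risk of 0.5. The 60% is for at- or below-level pain combined.

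**Inputs not in the documents (assumed):** sham rate for each pain type, effect per type, and correlation between types within a subject. I take a common relative risk of 0.5 (the plan's design effect), sham rates mainly 35–45%, and latent correlation 0–0.6. There is partial support for those rates. If at-level and below-level pain were equally common and independent, a combined 60% implies 1 − (1 − p)² = 0.60, so p = 1 − √0.40 = 0.37. At latent correlation 0.3 and 0.6 the same condition gives about 41% and 45%. The nociceptive rate has no such anchor.

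**Step 1. The plan's own figure.** Power of the pooled z test with n per arm:

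Φ{[|p1 − p2| − 1.96·√(2p̄(1 − p̄)/n)] / √[(p1(1 − p1) + p2(1 − p2))/n]}

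For 0.60 v 0.30, n = 41: (0.30 − 1.96 × 0.1099)/0.1048 = 0.81, power 79.0%. The unpooled form gives 81.7% and exact enumeration 81.3%. The stated 80% is reproduced.

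**Step 2. Power per type at relative risk 0.5, 41 per arm.**

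| Sham rate | 20% | 30% | 40% | 50% | 60% |
|---|---|---|---|---|---|
| Power | 0.24 | 0.37 | 0.51 | 0.65 | 0.79 |

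**Step 3. Chance of mixed significance with independent outcomes.** Two types: P1(1 − P2) + P2(1 − P1).
- 40/40%: 2 × 0.507 × 0.493 = 0.50.
- 60/20%: 0.790 × 0.757 + 0.243 × 0.210 = 0.65.
- No effect: 2 × 0.05 × 0.95 = 0.095.

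Three types: 1 − P(all significant) − P(none significant).
- 40% each: 1 − 0.507³ − 0.493³ = 0.75.
- No effect: 1 − 0.05³ − 0.95³ = 0.14.

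**Step 4. Allowing for correlation** (simulated trials, correlated binary outcomes from a multivariate normal, 41 per arm).

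| Setting | Mixed significance |
|---|---|
| Two types, sham 35–45%, both halved, correlation 0–0.6 | about 36–51% |
| Two types, sham 60/20%, both halved | up to about 66% |
| Three types, sham 40% each, all halved, correlation 0–0.6 | about 56–75% |
| No TENS effect | about 9–11% (two types), about 15% (three) |

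**Step 5. What a direct test does when relative risks are equal at 0.5.** The result depends on the scale.

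| Contrast between types | Sham rates | False-difference rate |
|---|---|---|
| Log relative risk | all settings tried, two or three types | about 3–5% |
| Risk difference | 35/45% | about 6.5–7.6% |
| Risk difference | 60/20% | about 33–45% |
| Odds ratio (logit) | 60/20% | about 9–11% |

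The reason is arithmetic. Going from 60% to 30% is an odds ratio of (0.30/0.70)/(0.60/0.40) = 0.29; from 20% to 10% it is (0.10/0.90)/(0.20/0.80) = 0.44. Equal relative risks are therefore unequal odds ratios and unequal risk differences when base rates differ.

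These calculations concern presence of pain; severity was not simulated.

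**The case against.** The strongest reply is that the plan never says a difference in significance will be taken as a difference in effect. Side-by-side estimates with intervals would satisfy the same sentence. That stands: a reader might infer that the significant-versus-not rule is planned, but the documents state no rule at all. The gap is the missing direct comparison, and the percentages show what follows if the gap is filled in the usual informal way.

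Second, a reader might take 36–51% as a property of this trial. It is not. The documents give no per-type rates, effects or correlations, and equal relative effects alone do not fix the figure: for two types it runs from about 9–11% with no effect to about 66%.

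Third, a reader might say that Aim 2 contains the same error. That is too strong. The differential question there is raised as a gap in the literature, Hypothesis 2b concerns neuropathic pain only, and the sentence on sub-analyses makes no differential claim. The point applies to Aim 2 only if such a claim is later made.

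Fourth, an interaction test has modest power here. If TENS halved one type (40% to 20%) and left another at 40%, simulated power is about 27–40%; on the log relative-risk scale it is somewhat higher but still under 50%. This is true, but low power to show a difference is a reason for caution and does not make separate tests a substitute.

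**Conclusion.** The point holds in this form: section 11 poses a question about differential effect and specifies no analysis that answers it, although a single model on data already collected would do so. The size is conditional. Under a common halving with 41 per arm and assumed sham rates of 35–45%, two separate tests disagree by chance in about 36–51% of trials, and three at 40% give a mixed result in about 56–75%. Even with no TENS effect the figures are about 9–11% and 15%. A direct test on the relative-risk scale gives about 3–5% under equal relative effects.

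These are supplementary analyses. Nothing here affects the primary two-proportion z test or the sample size. The change should be made before the data are analysed, but it is not critical to the trial's main conclusion.

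**What to change.** - Stack each subject's 12-month outcomes for the three pain types and fit one model per question, clustered on subject (for example GEE with robust variance), with arm, pain type and arm × pain type.
- Prespecify the effect scale. For presence, use a log link (relative risk) if equal relative effects is the null; a logistic or risk-difference model tests a different null when base rates differ. For severity, use a linear model. State how a subject without a given pain type is scored.
- Base any claim of differential impact only on the interaction, reported with its 95% CI. Report type-specific effects as descriptive estimates with CIs.
- For Aim 2, add a predictor × pain-type term if a differential claim is intended; otherwise label the sub-analyses by diagnostic category as descriptive.

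The cost is SAP wording and a slightly larger model, with no new data or visits. The drawback is that the interaction has modest power, so fewer differential claims will be made.
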